7.3.2 Other Efficacy Analyses

Additional quantitative efficacy parameters will be analyzed in the following way:

Analysis of CGI-I score, change from baseline in HAMD-17 total score, change from baseline in HAM-A total score, and change from baseline in CGI-S will be performed using a similar MMRM to that used for the primary analysis. Baseline CGI-S score will be used as a covariate for the analysis of change in CGI-I score. In addition, these parameters will be analyzed using ANCOVA (with LOCF imputation) as used for the analysis of primary efficacy parameters.

Additional categorical efficacy parameters will be analyzed in the following way:

Rates for categorical parameters (response and remission) will be reported by treatment group and by visit; a logistic regression model (with LOCF imputation) will be used to model the probability of a response or the probability of a remission as a function of a treatment group and the corresponding baseline score (CGI-S for the analysis of the CGI-I response) as explanatory variables.

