Dosing compliance for the background ADT during a specified period is defined as the dose actually taken by a participant during that period divided by the dose expected to be taken during the same period multiplied by 100. Descriptive statistics for ADT compliance will be presented for each ADT and overall by the double-blind investigational product treatment group for the period from the first dose of DB IP actually taken to the last dose of DB IP actually taken for the Safety Population.

9.0 **EFFICACY ANALYSES**

All efficacy analyses will be based on the mITT population. Baseline for efficacy is defined as the last non-missing efficacy assessment before the date of the first dose of DB IP. All statistical tests will be conducted at the $\alpha=0.05$ (2-sided) level for main effects. All confidence intervals (CIs) will be 2-sided 95% CIs, unless stated otherwise.

For efficacy analyses in which country is a factor, a *small country* will be defined as a country with fewer than 2 participants in at least one treatment group in the mITT Population. Small countries will be pooled to form pseudo-countries so that each treatment group includes at least 2 mITT participants within the country. Countries will be ranked on number of participants that are part of the mITT Population and lowest ranked countries will be pooled (sequentially, i.e., a new ranking is made after each step) until the smallest pooled country has reached at least 2 participants in each treatment group.

To compare with historic studies, some analyses based on the imputed data using the last-observation-carried-forward (LOCF) approach, will be presented for all efficacy parameters. Only the postbaseline total score of a parameter will be imputed; individual item scores will not be carried forward. The baseline value will be carried forward only for the intermittent missing values immediately after baseline. If all the postbaseline values are missing, the baseline value will not be carried forward.

9.1 **PRIMARY EFFICACY PARAMETER**

The primary estimand is provided below through specification of the population, the variable, the handling of intercurrent events, and the population-level summary.

Population

The target population are participants with MDD who have had an inadequate response to antidepressant therapy in the current episode and who satisfy the inclusion and exclusion criteria as specified in the protocol.

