The analysis population is defined to be the mITT population consisting of all randomized participants with ≥ 1 postbaseline assessment of the MADRS total score.

Variable

The variable is the primary efficacy endpoint, change from baseline to Week 6 in the MADRS total score.

Accounting of Intercurrent Events

Intercurrent events and their handling rules are described as follows:

- Regardless of whether allowed rescue medications are taken or not, data are included in the analysis. Participants are still taking assigned drugs as specified in the protocol while taking allowed rescue medications. The clinical objective is to assess the efficacy of the treatment regardless of allowed rescue medication use.
- To evaluate the efficacy at Week 6 in the mITT population, participants are assumed to adhere to the assigned treatment for the duration of the study. As a result, data after the discontinuation from the study treatment due to all reasons will not be included in the primary analysis and they will be assumed as missing at random.

Population-level Summary

The population-level summary for the primary endpoint is the difference in primary variable means between each cariprazine group and placebo.

To address the primary hypotheses that each dose of cariprazine is superior to placebo in the reduction of MADRS total score after 6 weeks of treatment, the change from baseline in MADRS total score will be analyzed using a mixed-effects model for repeated measures (MMRM) with treatment group, pooled country, ADT failure category (per CRF), visit, and treatment group-by-visit interaction as fixed effects, and the baseline value and baseline-by-visit interaction as the covariates. An unstructured covariance matrix will be used to model the covariance of within-participant scores. The Kenward-Roger approximation ([Kenward and Roger, 1997](#)) will be used to estimate denominator degrees of freedom. In the event of non-convergence of the model using unstructured covariance matrix, a structured covariance matrix will be used in combination with empirical variance estimate (i.e., sandwich estimator) to address the potential misspecified situation. The following sequence of alternative covariance structures (First-order ante-dependence [ANTE (1)], Toeplitz [TOEP], First-order autoregressive [AR (1)] and compound symmetry[CS]) will be considered in the MMRM until convergence.

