9.2 KEY SECONDARY EFFICACY PARAMETER

The key secondary endpoint is the change from baseline to Week 6 in the CGI-S score.

To test the secondary hypotheses that each dose of cariprazine is superior to placebo in the reduction of CGI-S score after 6 weeks of treatment, the change from baseline in CGI-S score will be analyzed using the MMRM approach similar to the one used for the primary analysis. A sensitivity analysis will also be performed using ANCOVA (with LOCF imputation) as used for the analysis of primary endpoint.

To control the overall familywise type I error rate at the 0.025 level (one-sided), a truncated Hochberg will be used for the primary endpoint, and the regular Hochberg procedure for the key secondary endpoint. The truncation parameter will be set to $\gamma = 0.9$ (Dmitrienko 2011).

The cariprazine dose groups will be labeled as Dose 1 (1.5 mg) and Dose 2 (3.0 mg).

The null hypotheses can be grouped into two families:

- (i) Family 1 includes the null hypotheses H_1 and H_2 for the primary endpoint:

H_1 denotes the null hypothesis of the difference in mean change from baseline in MADRS at Week 6 between cariprazine Dose 1 and placebo is ≥ 0 .

H_2 denotes the null hypothesis of the difference in mean change from baseline in MADRS at Week 6 between cariprazine Dose 2 and placebo is ≥ 0 .

- (ii) Family 2 includes the null hypotheses H_3 and H_4 for the key secondary endpoint:

H_3 denotes the null hypotheses of the difference in mean change from baseline in CGI-S at Week 6 between cariprazine Dose 1 and placebo is ≥ 0 .

H_4 denotes the null hypotheses of the difference in mean change from baseline in CGI-S at Week 6 between cariprazine Dose 2 and placebo is ≥ 0 .

The gatekeeping procedure utilizes the following decision rules:

- (i) Step 1. The null hypotheses in Family 1 are tested using the truncated Hochberg procedure at the full α level. Let $p_{(1)} < p_{(2)}$ denote the ordered p-values in Family 1 and let $H_{(1)}$ and $H_{(2)}$ denote the associated null hypotheses. The truncated Hochberg procedure rejects both $H_{(1)}$ and $H_{(2)}$ if $p_{(2)} \leq \alpha(1 + \gamma)/2$ or it rejects only $H_{(1)}$ if $p_{(1)} \leq \alpha/2$ and $p_{(2)} > \alpha(1 + \gamma)/2$.
- (ii) Step 2. The null hypotheses in Family 2 are tested as follows:

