9.3 ADDITIONAL EFFICACY PARAMETER(S)

Additional efficacy parameters will include the following at postbaseline visits described in [Table 3-2](#):

- Change from baseline in MADRS total score at Weeks 1, 2, 4
- Change from baseline in the CGI-S score at Weeks 1, 2, 4
- CGI-I score at Weeks 1, 2, 4, 6

- CGI-I response (CGI-I score ≤ 2) at Weeks 1, 2, 4, 6
- MADRS response ($\geq 50\%$ reduction from baseline in MADRS total score) at Weeks 1, 2, 4, 6
- MADRS remission (MADRS total score ≤ 10) at Weeks 1, 2, 4, 6
- Change from baseline in the HAMD-17 total score at Week 6
- Change from baseline in the HAM-A total score at Week 2, 6
- HAM-A response ($\geq 50\%$ reduction from baseline in HAM-A total score) at Weeks 2, 6
- HAM-A remission (HAM-A total score ≤ 7) at Weeks 2, 6
- Change from baseline in MADRS individual item scores at Weeks 1, 2, 4, 6
- Change from baseline in HAM-A individual item scores at Weeks 2, 6

Additional quantitative efficacy parameters will be analyzed in the following way:

Analysis of CGI-I score, change from baseline in HAM-A total score, change from baseline in MADRS and HAM-A individual item scores, and change from baseline in CGI-S will be performed using a similar MMRM to that used for the primary analysis. Baseline CGI-S score will be used as a covariate for the analysis of CGI-I score. In addition, these parameters will be analyzed using ANCOVA (with LOCF imputation) as used for the analysis of primary efficacy parameters.

Change from baseline in HAMD-17 total score will be analyzed based on ANCOVA model using observed cases, with treatment group, pooled country, and ADT failure category (per CRF) as factors and baseline HAMD-17 total score as a covariate for between-treatment-group comparisons at Week 6.

Additional categorical efficacy parameters will be analyzed in the following way:

Rates for categorical parameters (response and remission) will be reported by treatment group and by visit; a logistic regression model (with LOCF imputation) will be used to model the probability of a response or the probability of a remission as a function of a treatment group, pooled country, ADT failure category (per CRF) and the corresponding baseline score (CGI-S for the analysis of the CGI-I response) as explanatory variables.

10.0 **SAFETY ANALYSES**

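### Response and remission have LOCF logistic regression as their only model, out of line with the plan's own missing-at-random approach to the repeated quantitative endpoints

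*SAP*

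**What the plan says.** SAP 9.3 specifies for the categorical endpoints that "a logistic regression model (with LOCF imputation) will be used to model the probability of a response or the probability of a remission", adjusted for treatment, pooled country, ADT failure category and the relevant baseline score. Protocol 7.3.2 also has only an LOCF logistic model. The protocol lists CGI-I response, MADRS response and MADRS remission; the SAP adds HAM-A response and remission. Neither document plans a MAR-based, observed-case or non-responder analysis of any of them.

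On the tabulated figures, SAP 9.3 says only: "Rates for categorical parameters (response and remission) will be reported by treatment group and by visit". It does not say whether those rates use LOCF or observed data. SAP 15.2 codes everyone who is not a responder as 0, with no explicit rule for a missing score.

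Elsewhere the plan takes a different line:
- SAP 9.0 gives the role of LOCF: "To compare with historic studies, some analyses based on the imputed data using the last-observation-carried-forward (LOCF) approach" are to be shown for the efficacy parameters.
- CGI-I, CGI-S, HAM-A and the item scores get an MMRM, with LOCF ANCOVA in addition. HAMD-17, with one post-baseline visit, gets observed-case ANCOVA.
- In the estimand of SAP 9.1, "The variable is the primary efficacy endpoint, change from baseline to Week 6 in the MADRS total score". Data after treatment discontinuation "will not be included in the primary analysis and they will be assumed as missing at random".
- SAP 3.0 regards data missing because of COVID-19 as MAR and MAR-based models as appropriate for them.

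For the key secondary endpoint, CGI-S at Week 6, SAP 9.2 adds an LOCF ANCOVA as sensitivity analysis.

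**The concern.** The binary endpoints are the only efficacy endpoints for which the method kept for historical comparison is the sole analysis. A patient who stops after Week 1 or 2 enters the Week 6 logistic model as if improvement had frozen there. The MMRM on the same scale treats the later values as MAR. By SAP 15.2 the same freezing applies to missed and out-of-window visits, including those missed because of the pandemic. In the 3 mg/day arm, a score carried forward from Week 1 or 2 was obtained on 1.5 mg/day (SAP Table 3-1), yet it counts towards that arm's Week 6 result.

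Response and remission are figures that clinicians read directly. While patients are still improving, LOCF pulls both arms down. Its effect on the difference depends on which arm loses more patients and when. The two analyses of one scale could therefore disagree for reasons unrelated to the drug.

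**Working it through.** **1. The plan's own figures.** SAP 13.0 gives 250 per arm, effect size 0.286, 15% dropout at Week 6, within-person correlation 0.58, and power of 83% for each dose (84% in Protocol 7.7) and about 90% for at least one. The inflation formula is not stated. Taking 1 + [d/(1−d)](1−ρ²) = 1 + 0.1765 × 0.6636 = 1.117, effective n is 250/1.117 ≈ 224 and the expected test statistic is 0.286 × √(224/2) ≈ 3.03. With correlation 0.5 between the two comparisons, and with this or a compound-symmetry factor (1.10 to 1.12), Hochberg gives 83.8 to 84.4% per dose and 91.0 to 91.4% for at least one. The truncated version, without the re-test, gives 83.4 to 84.0% and 90.9 to 91.3%. The plan's figures reproduce within 2 points. It gives no rates or power for response or remission.

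**2. Inputs for the LOCF check.** From the documents: effect size 0.286, correlation 0.58, 15% dropout, and visits at Weeks 1, 2, 4 and 6. Assumed, because the documents do not give them: baseline MADRS mean 32, SD 5; Week 6 change SD 10; placebo improvement 12, hence active 12 + 0.286 × 10 = 14.86 (SAP 9.1 expects the mean reduction to be within 15 points); gradual improvement (35%, 58%, 85% and 100% of the Week 6 mean); dropout after Weeks 1, 2 and 4, more likely in worse patients. There were 400,000 simulated patients per arm. Response is a reduction of at least 50%; remission is a score of 10 or less.

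**3. Results (% placebo v active; difference in points).**

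| Dropout, placebo/active | Response, full data | Response, LOCF | Remission difference, full → LOCF | Unadjusted power for response, full → LOCF |
|---|---|---|---|---|
| 15/15% | 34.9 v 45.6 (10.7) | 32.4 v 42.0 (9.6) | 7.7 → 7.0 | 68% → 61% |
| 12/18% | 35.0 v 45.6 (10.5) | 33.0 v 41.2 (8.2) | 7.5 → 6.1 | 67% → 48% |
| 10/20% | 34.9 v 45.5 (10.7) | 33.2 v 40.8 (7.6) | 7.7 → 5.9 | 68% → 42% |
| 20/10% | 34.9 v 45.6 (10.7) | 31.4 v 43.3 (11.9) | 7.7 → 8.2 | 69% → 79% |

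Sequential-regression imputation under MAR within arm, then dichotomising, gave 34.9 v 45.5 (10.6) at 15/15% and 10.5 to 10.7 in the other rows. It recovers the full-data result.

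**4. Why the pattern arises.** LOCF rate = full-data rate − D × g, where D is the dropout proportion and g is the dropouts' shortfall between Week 6 and carried-forward response. From the first row, g = 2.5/0.15 ≈ 16.7 points (placebo) and 3.6/0.15 = 24.0 points (active). At 10/20% this predicts 10.7 − (0.20 × 24.0 − 0.10 × 16.7) = 7.6, as simulated. At 20/10% it predicts 10.7 − (0.10 × 24.0 − 0.20 × 16.7) = 11.6, against 11.9 simulated, because g shifts slightly with the dropout rate.

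**5. No true effect.** Equal dropout gives no bias in the difference. A 10-point imbalance gives about 0.10 × 16.7 = 1.7 points; the simulated values were 1.7 to 1.9, in either direction.

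**6. Sensitivity.** With improvement that plateaus earlier, the LOCF response difference is 9.8 (15/15%), 8.7 (12/18%), 8.0 (10/20%) and 11.8 (20/10%). At 15% equal dropout, the loss of about 1 point also held for placebo improvement of 11 to 12.5 and SD of 9 to 11.

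**The case against.** A reader might infer that LOCF here breaches the trial's own estimand. The documents do not support that: the only estimand has MADRS change as its variable. The fault is inconsistency of approach and a missing estimand. Declining to credit later improvement to patients who stopped is also a defensible question. LOCF does not answer it cleanly, however, because it still counts as a Week 6 responder someone who was responding when they stopped.

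A reader might also infer that the published rates will be LOCF rates. SAP 9.3 ties LOCF to the logistic model and leaves the basis of the rates open.

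On size, a loss of about a third can be produced (7.1 instead of 10.4 points) by assuming 12/18% dropout with the active dropout mostly early. The documents give one overall dropout figure and no split by arm or timing. At 15% in both arms the loss is about 1 point, against a standard error of √[(0.349 × 0.651 + 0.455 × 0.545)/250] ≈ 4.4 points. Protocol 8.8 also asks for the Visit 6/ET assessments at discontinuation. The simulation carries forward scheduled visits only and does not model these.

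Finally, the underlying MADRS, CGI-I and HAM-A scores all have an MMRM, so a reader can compare. These limits stand. They bound the concern but leave no reason for LOCF to be the only model.

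**Conclusion.** The point holds as an analysis choice worth correcting. LOCF is the sole model for five additional binary endpoints, although the plan gives it a historical role and uses MAR-based models for the repeated quantitative endpoints. If the target is the Week 6 outcome on assigned treatment, the expected cost at the planned dropout is about 1 point of response difference, towards no effect. Larger errors, in either direction, need dropout that differs by arm. All sizes rest on the assumed baseline, SD, time course and dropout pattern. The gatekeeping procedure covers MADRS and CGI-S change only, so the definition of a positive study is untouched.

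A secondary point concerns CGI-S. It would be too strong to say that LOCF ANCOVA is its only firm sensitivity analysis: SAP 5.5 excludes one site, and SAP 16.1 splits by randomisation date and repeats the analysis in patients who finished before the pandemic cutoff. None of these tests MAR. LOCF ANCOVA is the only firmly planned missing-data sensitivity analysis for CGI-S, and it does not probe MAR well. The copy-reference analysis in SAP 16.1 is optional.

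**What to change.** In SAP 9.3:
- State the estimand for response and remission.
- Make the main analysis of MADRS response and remission multiple imputation of the total score under MAR within arm, excluding post-discontinuation data as in the primary analysis, with 200 imputations as in SAP Appendix I. Then dichotomise, fit the stated logistic model in each dataset and combine by standard rules.
- Do the same for CGI-I and HAM-A with their own imputation models.
- Keep LOCF as the labelled historical comparison.
- State which data the tabulated rates use, and clarify in SAP 15.2 how a missing score is coded.

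For CGI-S, make the copy-reference analysis in SAP 16.1 firm. It depends on discontinuation for lack of efficacy, which Protocol 8.8 does not list among its reasons, so confirm that the eCRF records it. If a pattern-mixture analysis is added, set a shift range for the 7-point CGI-S. The 0 to 6 range in SAP 9.1 is in MADRS points and cannot be transferred.

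The cost is SAP wording, modest programming and a second set of rates to explain. Programming is heavier for CGI-I, which has no baseline value, and for HAM-A, measured after baseline only at Weeks 2 and 6, because imputation of additional-endpoint scores is specified only for MADRS.

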10.2 CLINICAL LABORATORY PARAMETERS

Descriptive statistics for clinical laboratory values (in SI units) and changes from the baseline values at each assessment time point will be presented by treatment group for the following laboratory parameters:

Hematology:	Absolute and differential white blood cell count, erythrocyte count, hemoglobin, hematocrit, platelet count, and red blood cell indices (mean corpuscular volume, mean corpuscular hemoglobin, and mean corpuscular hemoglobin concentration)
Chemistry:	Sodium, potassium, calcium, chloride, bicarbonate, glucose, blood urea nitrogen, creatinine, total protein, alkaline phosphatase, albumin, total bilirubin, direct bilirubin, indirect bilirubin, AST, ALT, free T3, free T4, TSH, lactate dehydrogenase, creatine phosphokinase, γ -glutamyl transpeptidase, uric acid, phosphate, lipid panel (total cholesterol, triglycerides, low-density lipoproteins, high-density lipoproteins), prolactin, insulin, and magnesium
Urinalysis:	Specific gravity, pH

In addition, descriptive statistics for values and changes from the baseline values in conventional units at each assessment time point will be presented for selected clinical laboratory parameters listed in [Appendix II](#). A description of reporting the lab values in conventional units in participant narratives (along with the standard reporting in SI units) is presented at the end of [Appendix II](#). Only participants with clinical laboratory data at baseline and at least one postbaseline visit during the double-blind period will be included in the summary.

Laboratory tests values are considered to be potentially clinically significant (PCS) if they meet either the low or high PCS criteria listed in [Table 10-1](#). The number and percentage of participants with PCS postbaseline clinical laboratory values will be tabulated by treatment group. The percentages will be calculated relative to the number of participants with available non-PCS baseline values and at least 1 postbaseline assessment. The numerator will be the total number of participants with available non-PCS baseline values and at least 1 PCS postbaseline value. A supportive listing of participants with PCS postbaseline values will be provided, including the participant identification number, study center number, and baseline and postbaseline values. A listing of all AEs occurring in participants who have PCS laboratory values will also be provided.

The number and percentage of participants with treatment-emergent significant changes in lipid parameters (total cholesterol, low-density lipoprotein cholesterol, high-density lipoprotein cholesterol, and triglycerides) and glucose will be tabulated by treatment group for the DB treatment period. The criteria for treatment-emergent significant changes in lipids and glucose is provided in [Table 10-2](#). Percentages will be calculated relative to the number of participants with baseline values meeting the specified baseline criteria and with at least 1 postbaseline assessment. The change in lipids and glucose from baseline to the highest (lowest for high-density lipoprotein cholesterol) postbaseline measurement will be summarized. Supportive listings of participants with treatment-emergent changes in lipids and glucose values will be provided.

The number and percentage of participants meeting potential Hy's Law criteria (elevation of alanine aminotransferase [ALT] or aspartate aminotransferase [AST] $\geq 3x$ ULN with total bilirubin [TBL] $\geq 2x$ ULN and alkaline phosphatase [ALP] $< 2x$ ULN in a 24-hour period) and Concurrent Elevations criteria in a 24-hour period will be tabulated by DB treatment group for the safety population. A supportive listing will be provided.

Concurrent Elevations in a 24-hour period are defined as:

1. ALT or AST $\geq 3x$ ULN and TBL $\geq 1.5 x$ ULN
2. ALT or AST $\geq 3x$ ULN and TBL $\geq 2 x$ ULN

Table 10-1 Clinical Laboratory PCS Criteria

Laboratory Parameter	SI Unit	PCS Criteria Low Values	PCS Criteria High Values
Hematology			
Hemoglobin	g/L	< 0.9 × LLN	—
Hematocrit	%	< 0.9 × LLN	—
Eosinophils	%	—	> 10
Neutrophils	%	< 30	> 90
Basophils	%	—	> 6
Monocytes	%	—	> 20
Lymphocytes	%	< 10	> 60
Absolute neutrophils	10 ⁹ /L	< 1.0	—
Platelet count	10 ⁹ /L	≤ 75	≥ 700
White cell count	10 ⁹ /L	≤ 2.5	≥ 15
Chemistry			
Albumin	g/L	< 0.9 × LLN	> 1.1 × ULN
Alkaline phosphatase	U/L	—	≥ 3 × ULN
ALT	U/L	—	≥ 3 × ULN
AST	U/L	—	≥ 3 × ULN
GGT	U/L	—	≥ 3 × ULN
LDH	U/L	—	≥ 3 × ULN
Blood urea nitrogen	mmol/L	—	> 1.2 × ULN
Calcium	mmol/L	< 0.9 × LLN	> 1.1 × ULN
Chloride	mmol/L	< 0.9 × LLN	> 1.1 × ULN
Cholesterol	mmol/L	—	> 1.3 × ULN
HDL	mmol/L	< 0.8 × LLN	—
LDL	mmol/L	—	> 1.2 × ULN
CPK	U/L	—	> 1.5 × ULN
Creatinine	μmol/L	—	> 1.3 × ULN
Glucose, fasting	mmol/L	< 0.8 × LLN	> 1.2 × ULN
Magnesium	mmol/L	< 0.9 × LLN	> 1.1 × ULN
Potassium	mmol/L	< 0.9 × LLN	> 1.1 × ULN
Sodium	mmol/L	< 0.9 × LLN	> 1.1 × ULN
Total bilirubin	μmol/L	—	> 1.5 × ULN
Total protein	g/L	< 0.9 × LLN	> 1.1 × ULN
Triglycerides, fasting	mmol/L	—	> 1.2 × ULN
Uric acid	μmol /L	—	> 1.1 × ULN
Urinalysis			
Protein	—	—	At least 2 +
Glucose	—	—	At least 2 +
Blood	—	—	At least 2 +

ALT = alanine aminotransferase; AST = aspartate aminotransferase; CPK = creatine phosphokinase; GGT = gamma glutamyl transferase; HDL = high-density lipoprotein; LDH = lactate dehydrogenase; LDL = low-density lipoprotein; LLN = lower limit of normal laboratory reference range; PCS = potentially clinically significant; SI = *Le Système International d'Unités* (International System of Units); ULN = upper limit of normal laboratory reference range.

Laboratory Parameter	SI Unit	PCS Criteria Low Values	PCS Criteria High Values
-----------------------------	----------------	------------------------------------	-------------------------------------

Fasting: Includes both, fasting and unspecified fasting status.

Table 10-2 The Criteria for Treatment-emergent Significant Changes in Lipids and Glucose

Laboratory Parameter	Measurement	Category	Criteria
Total cholesterol (Fasting or Non-fasting)	Actual	Normal	< 200 mg/dL
		Borderline	≥ 200 and < 240 mg/dL
		Normal/Borderline	< 240 mg/dL
		High	≥ 240 mg/dL
		Borderline/High	≥ 200 mg/dL
	Change from baseline	Increase ≥ 40 mg/dL	Increase ≥ 40 mg/dL
LDL Cholesterol* (Fasting)	Actual	Normal	< 100 mg/dL
		Borderline	≥ 100 and < 160 mg/dL
		Normal/Borderline	< 160 mg/dL
		High	≥ 160 mg/dL
		Borderline/High	≥ 100 mg/dL
	Change from baseline	Increase ≥ 30 mg/dL	Increase ≥ 30 mg/dL
HDL Cholesterol (Fasting and Non-Fasting)	Actual	Normal	≥ 40 mg/dL
		Low	< 40 mg/dL
	Change from baseline	Decrease ≥ 20 mg/dL	Decrease ≥ 20 mg/dL
Triglycerides (Fasting)	Actual	Normal	< 150 mg/dL
		Borderline	≥ 150 and < 200 mg/dL
		Normal/ Borderline	< 200 mg/dL
		High	≥ 200 mg/dL
		Very High	≥ 500 mg/dL
		Borderline/High/Very High	≥ 150 mg/dL
		≥ 1000 mg/dL	≥ 1000 mg/dL
	Change from baseline	Increase ≥ 50 mg/dL	Increase ≥ 50 mg/dL
Triglycerides (Non-Fasting)	Actual	Very High	≥ 500 mg/dL
		≥ 1000 mg/dL	≥ 1000 mg/dL
	Change from baseline	Increase ≥ 10 mg/dL	Increase ≥ 10 mg/dL
Serum Glucose (Fasting)	Actual	Normal	< 100 mg/dL
		Impaired	≥ 100 and < 126 mg/dL
		Normal/ Impaired	< 126 mg/dL
		High	≥ 126 mg/dL
	Change from baseline	Increase ≥ 10 mg/dL	Increase ≥ 10 mg/dL
Serum Glucose (Non-Fasting)	Actual	Normal	< 140 mg/dL
		Borderline	≥ 140 and < 200 mg/dL
		Normal/Borderline	< 200 mg/dL
		High	≥ 200 mg/dL
		Borderline/High	≥ 140 mg/dL
	Change from baseline	Increase ≥ 20 mg/dL	Increase ≥ 20 mg/dL

* LDL direct and LDL calculated are combined.

Fasting: Includes both, fasting and unspecified fasting status.

